FIGURE 7. Topography and OCT based total power & topography maps. This figure shows that our recovered OCT based surfaces are sufficiently accurate to represent astigmatic information even in corneas altered by LASIK. Before LASIK (top row), topography and OCT are comparable (A & B). After LASIK (bottom row), topography (D) shows an effectively spherical cornea because it is only measuring the ablated anterior surface. In the OCT map (E), residual corneal astigmatism is still present (lighter blue) likely due to the unchanged astigmatic posterior surface (C & F). The measured spherical change pre to post LASIK was: $\Delta MRx = 5.25$ D, $\Delta topo = 3.94$ D, $\Delta OCT = 5.63$ D. The surgically induced change in astigmatism was: $\Delta MRx = 2.80$ D, $\Delta topo = 2.04$ D, $\Delta OCT = 2.63$ D. These maps show the central 5 mm of the cornea.

time was unreliable due to motion artifacts from slow acquisition [36]. Current clinical SDOCT is faster, but its limited depth range prevents measurement of the pertinent biometry values used in this formula. Our whole eye system is faster than SDOCT and has the depth range necessary to measure all the pertinent biometry values required to take advantage of this formula.

After undergoing cataract surgery with an intra-capsular posterior chamber IOL of the surgeon's choice, we will measure the manifest refraction at the final, post-operative month 1 visit. From this post-operative manifest refraction, the IOL power required to have achieved an emmetropic (plano) result will be calculated [45]. We will then compare this calculated reference power to the predicted power from the SoC and OCT methods and determine a prediction error for each. Given that IOLs are only powered in discrete increments of 0.50 D, a "good" clinical outcome should be within 0.50 D of the target. Hence, we will compare the proportion of subjects in the two groups (SoC and OCT) who have

prediction errors within ± 0.50 D of the calculated reference. Though finer discrimination than 0.50 D would be desirable, we are limited by the resolution of the IOL at ± 0.50 D steps. We cannot insert a lens that is 20.13 D, for example, if that is the theoretical suggested power. Reporting results within ± 0.50 D is also a standard accepted and used by the refractive surgical community [48].

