From the literature, we can estimate the expected proportions for the SoC (P_{SoC}) and OCT (P_{OCT}) groups. Using the Haigis-L, the proportion of subjects who had a result within ± 0.50 D of the calculated reference was approximately $P_{SoC} = 41.98\%$ [45,49]. In a small pilot using averaged 2D corneal SDOCT measurements with less sampling than our 3D reconstructions, Tang et al. found the proportion of subjects with a result within ± 0.50 D of the calculated reference to be $P_{OCT} = 68.75\%$. Our null hypothesis is OCT will equal SoC ($H_0: P_{SoC} - P_{OCT} = 0$), and the alternate hypothesis is that OCT will be different ($H_A: P_{SoC} - P_{OCT} \neq 0$). Proportions will be compared using a conditional McNemar's test for paired proportions. Using the estimated proportions, $\alpha = 0.05$, and assuming zero correlation between pairs, we will need a minimum of 60 subjects to complete the study to have 80% power to detect a significant difference between these two proportions (PROC POWER, SAS v.9.3). If the correlation between pairs is 0.2, 60 subjects will provide 88% power; if the correlation is as high as 0.4, the power will be 96%. To account for possible enrollment losses from intra-surgical complications or follow-up losses, we will target an enrollment of 65 subjects over the project period to ensure that we will meet the minimum of 60 completed study subjects.

In addition to the primary outcome measure above, we will additionally report the mean absolute prediction error for the two groups. We will also repeat the optical biometry and OCT imaging post-operatively to further study the relationship between pre-operative biometry and the final IOL position (ELP). These measurements will allow us to further characterize the relationship between clinical optical biometry and the whole eye OCT pre- and post-operatively.

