SA2. Expected Outcomes. We will have developed algorithms to accurately measure anterior segment biometry and corneal power with the whole eye OCT system. We will further have clinical data to support the idea that accurate measurement of anterior segment biometry will improve cataract surgery refractive outcomes in those who have previously had laser refractive surgery. While this growing population would particularly benefit because of the unique challenges presented by their altered corneas, the developed algorithms can also be applied for the larger group of cataract surgeries in those with normal corneas as well. Finally this aim also complements the posterior segment aim by independently validating the measurements of anterior segment surfaces by the whole eye OCT system.

SA2. Potential Problems & Alternative Strategies. While we expect that improved anterior segment biometry measurement with OCT will improve cataract surgery outcomes in those with prior LASIK, additional parameters could potentially further reduce the IOL prediction error. For instance, as described earlier, modern

[figure not shown]

FIGURE 8. Overview of primary clinical outcome to determine if more accurate anterior segment biometry measurement from OCT improves post-LASIK cataract surgery refractive outcomes. Before cataract surgery (left column), we will calculate the needed intraocular lens (IOL) power via (1) standard of care (SoC: 21.0 D in this example) and via (2) our OCT based corneal power and anterior segment biometry measurement (20.5 D). The surgeon will perform cataract surgery and implant an IOL (21.0 D IOL). Based on the post-operative refraction, the power actually needed for a plano result will be calculated (20.25 D). The difference between this calculated reference and the predicted power is the prediction error. We will compare the proportion of SoC and OCT results with prediction errors ≤ 0.50 D.

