While the natural lens does present an ambiguity, by first imaging pseudophakic subjects in group 1 and part of group 2, we will first refine and validate our algorithms independent of the natural lens. This lays the foundation for subsequently investigating and isolating any differences between MRI and OCT resulting from imaging phakic subjects in group 2. Our preliminary algorithm using a polynomial gradient index lens model [52] demonstrated reduced differences between OCT and MRI [4]. Alternate OCT based natural lens models [55] can be incorporated into our reconstructions for reanalysis of captured and stored image data if necessary. Our use of these gradient indices is far more sophisticated than the average refractive indices successfully used for ocular axial biometry both in research and clinically [56,57 and commercially available partial coherence interferometers]. If necessary, we can similarly use average indices. Importantly, with the validated pseudophakic group, we will be able to compare and contrast quantitative performance of OCT in phakic subjects. This data has important implications for both the OCT and myopia communities.

Timetable. We anticipate this ambitious project will require the full requested five year project period to complete. We anticipate the whole eye SSOCT system design and assembly will take approximately one year. Algorithm development will begin with initial images of phantoms and normals and can occur concurrently with clinical imaging because all acquired images can be post-processed at a later date if necessary. Data collection, data analysis, and publication will occur on a rolling basis throughout the project.

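### The plan does not state that the month-1 refraction is masked to the two predicted lens powers, or that the OCT prediction is locked before that refraction is known

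*Combined protocol and SAP*

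**What the plan says.** SA2. Research Design, Clinical study, derives the primary outcome from a single measurement after surgery: "we will measure the manifest refraction at the final, post-operative month 1 visit". The lens power that would have given a plano result is back-calculated from that refraction. Each method's prediction error is its distance from this one reference, and a success is an error of at most 0.50 D. The Figure 8 legend repeats the step with an example: "Based on the post-operative refraction, the power actually needed for a plano result will be calculated (20.25 D". The same legend has the SoC and OCT powers calculated before surgery.

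The analysis is paired: "Proportions will be compared using a conditional McNemar's test for paired proportions". It is two-sided, since "the alternate hypothesis is that OCT will be different". On size, "we will need a minimum of 60 subjects to complete the study to have 80% power".

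The documents do not say who performs the month-1 refraction or whether that person can see either predicted power. They describe no masking, independent refractionist, objective refraction or locking of predictions for this outcome. The Timetable lets algorithm development run alongside clinical imaging because "all acquired images can be post-processed at a later date if necessary". SA2. Potential Problems & Alternative Strategies adds regression on the collected data as a possible alternative approach.

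**The concern.** A manifest refraction is subjective, and under Figure 8 both predictions already exist when it is taken. Two routes to bias are therefore open.

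- **Refraction route.** A refractionist who knows the predictions could settle on an end point that brings the reference closer to one of them.
- **Reprocessing route.** OCT images reprocessed after the refraction is known could move the OCT prediction toward the reference. The SoC power comes from a public calculator and would stay where it is.

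A shared reference does not by itself cancel such bias. Moving it toward one prediction always shrinks that method's error, but it shrinks the other's only when both predictions lie on the same side. With a hard cut at 0.50 D, small movements change which pairs are discordant, and McNemar's test uses only those pairs. At stake is the only powered comparison in Aim 2.

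**Working it through.** **Inputs from the plan.** SoC success 41.98%, OCT success 68.75%, difference 26.77 points; two-sided alpha 0.05; conditional McNemar test; 60 completers; pair correlations 0, 0.2 and 0.4 (all SA2. Research Design, Clinical study). One refraction step is 0.25 D (SA2. Justification & Feasibility).

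**Step 1: reproduce the plan's power.** The sizing case is "Using the estimated proportions, $\alpha = 0.05$, and assuming zero correlation between pairs". Let p10 be the probability that only OCT succeeds and p01 that only SoC does. The number of discordant pairs is Binomial(60, p10+p01), followed by an exact two-sided binomial test against 0.5.

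- Correlation 0: both succeed with probability 0.4198 × 0.6875 = 0.2886, so p10 = 0.6875 − 0.2886 = 0.3989 and p01 = 0.4198 − 0.2886 = 0.1312. Power is 78.7% (stated 80%).
- Correlation 0.2: the joint probability rises by 0.2 × √(0.4198 × 0.5802 × 0.6875 × 0.3125) = 0.0458. Power is 87.4% (stated 88%).
- Correlation 0.4: power is 96.1% (stated 96%).

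The smallest n for 80% power is 62, against 60 stated. The plan's figures reproduce closely.

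**Step 2: set up no true difference.** Assume that both methods have normal, unbiased errors with 41.98% within 0.50 D. Then SD = 0.50 / Φ⁻¹((1 + 0.4198)/2) = 0.904 D. Assume also that a dioptre of refraction moves the reference by a dioptre of lens power, and that predictions are not rounded. With no bias, the chance of a significant result at n=60 is about 3%.

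**Step 3: refraction route.** Move the reference by up to 0.25 D toward the OCT prediction in every eye, without overshooting. OCT then succeeds whenever its unshifted error is within 0.75 D: 2Φ(0.75/0.904) − 1 = 59%. SoC moves with the shared reference. Simulated pairs, put through the Step 1 test, give:

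| Error correlation | Pair correlation | OCT | SoC | Difference (points) | Share of 26.77 | False-positive chance |
|---|---|---|---|---|---|---|
| 0 | 0 | 59.4% | 40.7% | 18.7 | 70% | 45% |
| 0.5 | 0.09 | 59.4% | 45.4% | 14.0 | 52% | 27% |
| 0.7 | 0.21 | 59.4% | 48.4% | 11.0 | 41% | 19% |
| 0.8 | 0.32 | 59.4% | 50.8% | 8.6 | 32% | 14% |
| 0.9 | 0.50 | 59.4% | 54.6% | 4.8 | 18% | 7% |

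Error correlation refers to the dioptre errors. Pair correlation refers to the success/failure results before any lean, which is the scale that the plan uses. Its 0.4 falls between the last two rows. Repeat simulations differ by about a percentage point.

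**Step 4: milder or opposite leans.**

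- A lean of 0.125 D in every eye gives about 35% of the planned difference at pair correlation 0 (false-positive chance 13%) and about 20% at 0.2 (7%).
- A 0.25 D lean in only half the eyes gives about 34% and 20%.
- If the planned effect is real and the lean is toward SoC, the 26.8 points shrink to about 4 (error correlation 0) or 14 (0.5).
- If 0.25 D of refraction moved the reference by 0.35 D, the shares in Step 3 would be 95%, 71% and 56% at error correlations 0, 0.5 and 0.7. The documents give no conversion.

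**Step 5: reprocessing route.** Pull the OCT prediction up to 0.25 D toward a known reference and leave SoC alone. The false gain is 59.3 − 41.98 = 17.3 points, and 17.3/26.77 = 65%, whatever the correlation. The false-positive chance is about 40%, 43%, 50% and 57% at error correlations 0, 0.5, 0.7 and 0.8.

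**The case against.** The strongest reply has four parts.

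1. **Silence is not evidence of an unmasked refraction.** A reader might infer that the refractionist will see the predictions. The documents do not say so, and they support only that masking is not stated. This stands.
2. **The shared reference gives real protection.** In the Figure 8 example the errors are 21.0 − 20.25 = 0.75 D for SoC (failure) and 20.5 − 20.25 = 0.25 D for OCT (success). Move the reference 0.25 D toward OCT, to 20.5 D: SoC's error becomes 0.50 D, which also counts as success, and OCT's advantage in that eye disappears. Both predictions lie on the same side of the reference in about 75% of eyes at error correlation 0.7. Positive correlation is plausible because both methods share an eye and a reference. This also stands, and it is why the share falls down the table. It does not apply to reprocessing.
3. **The bias modelled is demanding.** A general habit of refracting a little myopic or hyperopic is not a lean toward OCT. The scenario needs an eye-specific shift in a consistent direction. This stands as a limit on size.
4. **The Timetable sentence is a project-wide remark.** Figure 8 places both calculations before surgery, and the Clinical study section names a published vergence formula for OCT. This stands in part: nothing says that the pre-surgery OCT value is final, and development alongside clinical imaging is expressly allowed.

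**Conclusion.** The gap is real: neither masking of the month-1 refraction to the two predictions nor a lock on the OCT prediction is stated, and the only powered Aim 2 test depends on both. It is more than missing detail, because a team could follow the text exactly and still leave the comparison open to bias.

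A reader might go further and infer that a quarter-dioptre lean would create most of the planned effect, or that type I error is inflated. The documents do not support either. More than half of the planned difference from refraction bias needs close to a full-step lean toward OCT in nearly every eye, together with weakly correlated errors. At the plan's own correlation of 0.2 the share is about 41%, and at 0.4 it lies between 18% and 33%. Inflation is conditional on direction, since a lean toward SoC would cost power instead. The reprocessing route does reach about 65% at any correlation, but its 0.25 D pull is equally assumed.

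All sizes rest on equal true accuracy, normal unbiased errors, unrounded predictions, 1:1 conversion of refraction to lens power, and an assumed size, direction and frequency of bias. The omission and its remedy do not depend on those values.

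**What to change.** Add two statements to SA2. Research Design, Clinical study:

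- The person performing the month-1 manifest refraction is not shown the SoC or the OCT predicted power.
- For each eye, the SoC and OCT predicted powers are computed and recorded with a date before that refraction is released to the OCT analysts. The primary analysis uses those recorded values, and any later reprocessing or regression is exploratory.

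The cost is a masking instruction and a dated record, with the same visit and no added subjects; n=60 is unchanged. The one real downside is small: algorithm improvements that come after an eye's prediction is recorded cannot enter the primary analysis for that eye, although they can still be reported. Masking has to be in place before the first month-1 refraction, because it cannot be restored afterwards.

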The spatial inaccuracy of current posterior eye OCT images results from the current standard practice of simply displaying A-scans next to each other in a parallel fashion. This fails to account for the actual, non-parallel transit of OCT light through the eye. The objective of this aim is two-fold. The *first objective* is to develop and validate algorithms for accurately portraying the posterior eye in OCT images by ray tracing the OCT imaging paths through the imaged anterior eye. The *second objective* is to then test the hypothesis that corrected posterior eye OCT images will be comparable to MRI of the same eyes.

The *rationale* for this aim is that successful completion of this aim will produce posterior eye OCT images faithful enough to replace MRI imaging for studying posterior eye shape biomarkers. Our expectation is that this development will remove cost and logistical barriers limiting more widespread study of posterior eye shape as a diagnostic biomarker for myopia progression, particularly in children and young adults.

SA3. Justification & Feasibility. In an initial study by the P.I. [4], we enrolled subjects in an IRB approved study who had recently obtained head MRIs for their medical care but did not have ocular disease. We performed ocular biometry and retinal

[figure not shown]

FIGURE 9. Representative original and spatially (numerically) corrected retinal OCT B scans (top R) and comparison to MRI (bottom L and R) [4]. The posterior eye appears flat in the original image (top L) and has a more plausible physiologic curvature after spatial correction (top R). Reported values in the literature for posterior eye curvature (R_c) range from 10.8-14.1 mm [34]. Spatial correction in the 10 eyes in this study significantly reduced the difference between OCT and MRI posterior eye shape (bottom L). In this small preliminary study, there remains a bias and a possible trend between the OCT measures and MRI (bottom R).

SDOCT on these subjects. Using commercial ray tracing software, we modeled the commercial SDOCT system and the subjects' eyes using their measured biometric data. The spatial orientation of the OCT scan paths was then used to reorient each OCT A-scan to its modeled location in MATLAB. Using this correction, there was a significant reduction in differences and variability between posterior eye shape measured by OCT and MRI (Fig. 9).

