Despite the overall improvement in posterior eye OCT shape in this pilot study, there remained a bias between the OCT measures and MRI. The possible sources of error in this preliminary work (other than small

sample size) include the lower resolution of these non-orbital MRI scans, the use of schematic model anterior eyes, motion errors, and the unknown system-to-cornea distance to control for scan magnification.

In this proposal, we will perform a prospective study with dedicated orbital MRIs, with measured and model-free determination of all ocular surfaces, with decreased patient motion from the faster SSOCT system, and with direct measurement of the system-to-cornea distance (see SA1.Research Design.System Calibration). With these improvements, we anticipate that we will decrease the curvature difference between MRI and OCT to less than a millimeter (resolution of our MRI). Further, we will compare surface topographies of myopic patients with known morphometric changes (e.g. staphylomas) imaged with MRI and OCT.

SA3. Research Design. Algorithm development and validation. We will extend our previously developed three-dimensional refraction correction algorithms [20] to perform ray tracing of the OCT scan paths through the ocular surfaces contained within the whole eye OCT images. The anterior eye image content will be segmented and corrected of optical distortions as in Aim 2 (refraction, non-telecentricity, motion). Group refractive indices for our light source ($\lambda_0 = 1060$ nm) will be used for refraction correction as described in detail in SA2.Research Design.Algorithm Development. For the lens, we will measure the group index for IOLs, and use a polynomial model for natural lenses [52] as was used in our pilot work [4]. The retinal layers of the posterior eye will also be segmented in preparation for post-processing [53]. With a known system topology, measured and hence known system-to-cornea distance per patient, and an accurate representation of the anterior eye components, we will determine the spatial orientation of the OCT scan paths to the posterior eye. With these OCT scan paths, the posterior eye A-scans will be properly repositioned spatially to restore anatomic accuracy.

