We will validate the algorithms by imaging a constructed model eye. The model consists of a custom-made +30 D rigid gas permeable contact lens (Essilor, center thickness 490 μm), a +20 D intraocular lens (SA60AT, Alcon), and a glass hemisphere with a 12.5 mm radius of curvature (64-496, Edmund Optics). These will be mounted into a lens tube at physiological distances and then immersed into balanced salt solution, leaving only the anterior surface of the contact lens ("cornea") exposed. The model eye will be imaged with the whole eye OCT and the surfaces recovered. After correction with the above algorithms, the curvature of the hemisphere will be compared to that of the manufacturer reference.

Clinical study. For the clinical studies, we will enroll two groups of subjects: 1. pseudophakic subjects with no known history of ocular pathology other than refractive error (no more than -6 D) and 2. pseudophakic and phakic subjects with high progressive myopia including those with staphylomas.

Group 1. The goal for the first group is to demonstrate in a normal eye the ability to accurately recreate the posterior eye with OCT spatially comparable to MRI (Fig. 10). We will only include monofocal pseudophakic individuals in this group. This reduces uncertainties by using a known manufactured lens. At the Duke Eye Center, the monofocal lens of choice is manufactured by Alcon, and the company has provided us with the optical prescriptions of their IOLs for research use under a non-disclosure agreement. With the optical properties of the IOL known, we anticipate being able to fully characterize these normal, pseudophakic eyes optically. This also provides a baseline from which phakic eyes can be studied.

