Each enrolled subject will undergo the following imaging: optical biometry (LenStar, Haag-Streit), whole eye OCT, and MRI imaging. MRI will be performed on the clinical research scanners at the Duke Brain Imaging and Analysis Center (see support letter from director [name]). Annually, with the assistance of dedicated research coordinators, they image over 2000 subjects with MRI for over 70 research projects. Their scanner (GE) has a magnetic field strength of 3.0 Tesla. A high resolution T1 FSPGR sequence will be used to acquire images of the subject's eyes. Images will be acquired in the axial plane, with FOV=25.6cm, TR=8ms, TE=3ms, flip angle=12, 512x512x50 imaging matrix, completely covering the eyes. A second T2 weighted sequence will be acquired at the same slice prescription with TR=3s and TE=25ms. With these scan parameters, each voxel will be 0.5 mm^3 . During scanning, a fixation target will be provided to minimize eye motion during acquisition.

[figure not shown]

FIGURE 10. General overview of clinical study design to determine the difference between OCT and MRI posterior eye images. Using radius of curvature as a general measure of shape, we will compare the paired differences between the two modalities. In a second study in subjects with staphylomas, we will use root mean square difference to describe the topographic differences between the two registered modalities.

The radius of curvature of the posterior eye will be measured via surface fitting of the posterior eye data from OCT and MRI. To have 80% power to detect a 0.5 mm difference in radius of curvature between OCT and MRI using a paired one-sample t-test, we will need to enroll a minimum of 48 normal pseudophakic subjects (PROC POWER, SAS v9.3). This power calculation assumes that with our whole eye OCT and improved algorithms, we will halve the standard deviation of the difference between MRI and OCT found in our initial study (2.3 mm), resulting in an estimated standard deviation of 1.2 mm. At a 0.5 mm difference, we will be at the effective voxel resolution of the MRI scans and should also have more than enough resolution to identify the large-scale topographic abnormalities noted in previous MRI studies of myopia [25,26].

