Group 2. After enrollment and data analysis of the first group, we will then examine the ability of OCT to provide spatially comparable images to MRI in eyes that are structurally abnormal. We will enroll 20 adult patients with progressive high myopia (more than -6 D) especially targeting those with posterior staphylomas – outpouchings of the posterior eye. These subjects can be pseudophakic or phakic. Phakic subjects will be required to be cyclopleged to ensure no dynamic lens changes during imaging. For phakic reconstructions, we will use age appropriate models of the natural lens indices as we have used in our previous study [52]. After recovery of the OCT and MRI surfaces, the OCT surface will be registered to the MRI surface at a common feature (e.g. optic nerve) and via cross-correlation. A root mean square deviation across the registered surfaces will then be calculated to quantify the topographic difference between the OCT and MRI surfaces.

SA3. Expected Outcomes. At the conclusion of this aim, we will have developed algorithms to spatially correct full eye OCT images and validated them with reference phantoms. We will also have tested the idea that spatially corrected OCT images will be comparable to MRI representations of the posterior eye first in pseudophakic normal eyes and then in pseudophakic and phakic myopic eyes. This will provide the basis for OCT to replace MRI for ophthalmic studies of ocular morphometry, lowering cost and logistical barriers to these types of studies while also providing higher resolution images over MRI. This has clinical utility for study of myopia progression and risk stratification based on prior studies associating deviations in ocular shape with pathologic myopia.

SA3. Potential Problems & Alternative Strategies. The FOV of our proposed posterior eye OCT channel will be 85° (or ~120° relative to center of the eye) – at least double that of standard retinal photography. This should be sufficient for measuring posterior eye shape as it encompasses the entire macula and reaches nearly to the equator of the eye. Should larger FOV be desired, though, we can use montaging as others have shown with OCT [54] to further increase our FOV. Because our whole eye OCT also concurrently images the anterior eye, our reconstructions can account for the relative change in position between the system and the eye to increase the accuracy of montaging and provide additional references for montage reassembly.

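### Aim 3 Group 1 sets out to show that OCT is comparable to MRI, but names only a t-test for a difference and fixes no margin for comparability

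*Combined protocol and SAP*

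**What the plan says.** The second objective of Aim 3 (SA3. Introduction) is to "test the hypothesis that corrected posterior eye OCT images will be comparable to MRI of the same eyes". In SA3. Research Design, Clinical study, the goal of Group 1 is to "demonstrate in a normal eye the ability to accurately recreate the posterior eye with OCT spatially comparable to MRI". SA3. Expected Outcomes draws the consequence from the phantom work and both groups together: "This will provide the basis for OCT to replace MRI for ophthalmic studies of ocular morphometry".

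For Group 1 the outcome is the radius of curvature of the posterior eye, measured by both methods in the same eye. The one inferential method named stands in the sample-size sentence: "To have 80% power to detect a 0.5 mm difference in radius of curvature between OCT and MRI using a paired one-sample t-test", with a minimum of 48 subjects. The SD behind it assumes that "we will halve the standard deviation of the difference between MRI and OCT found in our initial study (2.3 mm"), which the plan rounds to 1.2 mm. Figure 10 describes the study as a "General overview of clinical study design to determine the difference between OCT and MRI posterior eye images", using paired differences.

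Two figures for closeness appear:
- The Group 1 text says "At a 0.5 mm difference, we will be at the effective voxel resolution of the MRI scans".
- SA3. Justification & Feasibility anticipates that "we will decrease the curvature difference between MRI and OCT to less than a millimeter (resolution of our MRI").

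Neither is stated as an equivalence margin, a confidence interval bound or a limit of agreement. No alpha is given for Aim 3.

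**The concern.** Comparability is a claim of closeness. A paired t-test of zero difference can reject, which shows a difference, or fail to reject, which does not by itself show closeness. It also responds the wrong way to poor precision: the noisier the OCT-MRI difference, the more often a real bias goes undetected. A precise method with a small and perhaps unimportant bias would tend to be declared different.

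Group 1 is the only part of Aim 3 with a sample-size calculation, so most of the statistical weight of the replacement claim rests on it. If no margin is fixed beforehand, what counts as comparable can be settled after the differences are seen, and the conclusion would then not be confirmatory.

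**Working it through.** **Inputs.** From the Group 1 text: n = 48, difference 0.5 mm, planning SD of the paired difference 1.2 mm, pilot SD 2.3 mm (exact half 1.15 mm). Assumed, because Aim 3 states neither: two-sided alpha 0.05 for the t-test, and 5% on each side for equivalence (a 90% CI). Normal differences are assumed throughout.

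**1. The plan's own figure.** The standard error is 1.2/√48 = 0.173 mm, the noncentrality 0.5/0.173 = 2.89, and the critical t on 47 df 2.012. Noncentral-t power is 80.7% at n = 48 and 79.9% at n = 47. The stated 48 reproduces.

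**2. How often the t-test misses a real bias, n = 48.**
- SD 1.2 mm, bias 0.5 mm: 1 − 0.807 = 19% non-significant.
- SD 2.3 mm, bias 0.5 mm: standard error 0.332 mm, noncentrality 1.51, power 31%, so 69% non-significant.
- SD 2.3 mm, bias 1.0 mm: 16% non-significant.
- The reverse case, SD 0.6 mm and bias 0.25 mm: the t-test rejects 81% of the time, while a ±0.5 mm equivalence rule is met 88% of the time.

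**3. Power of n = 48 for equivalence.** The rule is met if |mean difference| + t × s/√48 < margin, where s is the sample SD and t = 1.678 (95th percentile on 47 df). At the assumed SDs the CI half-width is 1.678 × 0.173 = 0.291 mm (SD 1.2) and 1.678 × 0.332 = 0.557 mm (SD 2.3). The second already exceeds 0.5 mm, so a ±0.5 mm rule can then hardly ever be met. Exact power, integrating over the sample SD:

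| SD (mm) | Margin (mm) | Bias 0 | 0.1 mm | 0.2 mm | 0.25 mm |
|---|---|---|---|---|---|
| 1.2 | ±0.5 | 77% | 70% | 52% | 41% |
| 1.2 | ±1 | >99% | >99% | >99% | >99% |
| 2.3 | ±0.5 | 1% | 1% | 1% | 1% |
| 2.3 | ±1 | 81% | 80% | 74% | 70% |

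**4. Subjects for 80% equivalence power at ±0.5 mm.** SD 1.2 mm: 51 at zero bias, 60 at 0.1 mm, 144 at 0.25 mm. SD 2.3 mm: 183 at zero bias. At ±1 mm and zero bias, 14 (SD 1.2 mm) or 47 (SD 2.3 mm) suffice.

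**5. Individual eyes.** At SD 1.2 mm and zero bias, the 95% limits of agreement are ±1.96 × 1.2 = ±2.35 mm. With n = 48, each limit has a 95% CI half-width of 2.012 × 1.2 × √(1/48 + 1.96²/(2 × 47)) = 0.60 mm. Part of this spread is MRI error, but a test on the mean does not address it.

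**The case against.** **The test is not misused in the text.** A reader might infer that the sponsor will treat p > 0.05 as proof of comparability. The documents do not say so. The t-test appears only in the sample-size sentence, and Figure 10 reads as estimation. The document is also a funding proposal, where an interval rule may simply be unwritten. This stands, and it makes the defect a missing decision rule. The aim still says that comparability will be tested and demonstrated, and nothing turns the estimate into that conclusion.

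**Non-significance is informative at the planning SD.** A non-significant mean is below 2.012 × s/√48, so its 90% CI ends below (2.012 + 1.678) × s/√48 = 0.533 × s. That is within 1 mm whenever the sample SD is under about 1.88 mm. This is correct, but it depends on the SD being nearly halved, which is itself an assumption, and it works only by adopting a margin that the plan does not set.

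**The two figures are not competing rules.** The sub-millimetre figure is an expectation about improving on the pilot, and a 0.5 mm difference satisfies it. This stands. What needs reconciling is that both are tied to MRI resolution and differ. At a true bias of 0.5 mm and SD 1.2 mm, the ±0.5 mm rule would be met 5% of the time and the ±1 mm rule 88%. This is the boundary case: 5% is the error rate of the ±0.5 mm rule by construction. At zero bias the contrast is 77% against more than 99%.

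**Two further readings go too far.** The limits of agreement should not be set against the 10.8–14.1 mm literature range in Figure 9, because the plan does not say whether those are study means or single eyes. Nor do the documents say that the algorithm will be tuned to MRI. The method is ray tracing through measured surfaces, checked on a model eye. SA3. Potential Problems says only that imaging Group 1 will help improve as well as validate the algorithms, which calls for a clarification.

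**Conclusion.** The concern holds as a missing decision rule: the only named test cannot establish the stated conclusion, and no margin is fixed. It should be corrected before Group 1 data are analysed. The sample size is not wrong on its own terms; 48 is right for the t-test described.

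Whether 48 is also enough for comparability depends on the margin, the SD and the residual bias. It is close to enough for ±0.5 mm if the SD is 1.2 mm and bias is near zero, ample for ±1 mm at that SD, and nearly useless for ±0.5 mm if the pilot SD persists. Residual bias cannot be dismissed, since the pilot left a bias and a possible trend (Figure 9). The figures rest on the assumed alpha levels and on normal differences.

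**What to change.** Before Group 1 data are analysed:

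1. Make the primary analysis a paired equivalence analysis. Conclude mean comparability only if the 90% CI of the mean OCT-MRI difference in radius of curvature lies within one margin. The sponsor should justify that margin after reconciling the two statements of MRI resolution. Keep the t-test as a secondary check for bias.
2. State the alpha, and restate the power of n = 48 for the chosen margin across the SDs and residual biases tabulated above.
3. Report Bland-Altman 95% limits of agreement with their CIs, and a regression of the difference on the pair mean to look for the trend suggested by the pilot. Limit the conclusion to mean agreement unless limits for individual eyes are also set.
4. As a secondary clarification, state that the algorithm version used for the primary comparison is fixed before Group 1 OCT results are compared with MRI. No eyes need to be set aside.

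The cost is protocol wording, a sponsor decision on the margin and a version lock. Imaging and enrolment can stay as they are. The price is a less favourable power statement if the margin is ±0.5 mm, where 80% power would take 51 to 144 subjects at SD 1.2 mm (bias 0 to 0.25 mm) and 183 at SD 2.3 mm with no bias. The plan should state that power openly; a larger enrolment is not being asked for.
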